6. MILESTONES

Milestone	Planned date
Submission of study protocol for Pharmacovigilance Risk Assessment Committee (PRAC) approval	28 November 2022
Approval of study protocol by PRAC	To Be Determined
Registration in European Union Post-Authorisation Study (EU PAS) Register*	At time of PRAC approval of protocol
Start of data collection/first patient enrolled*	Within 6 months after PRAC approval
Last patient enrolled*	5 years after start of enrolment
End of data collection*	10 years after start of data collection
Study progress report*	Year 1 after start of data collection
Study progress report*	Year 2 after start of data collection
Study progress report*	Year 3 after start of data collection
Interim report of study results*	Year 4 after start of data collection
Study progress report*	Year 5 after start of data collection
Study progress report*	Year 6 after start of data collection
Study progress report*	Year 7 after start of data collection
Interim report of study results*	Year 8 after start of data collection
Study progress report*	Year 9 after start of data collection
Study progress report*	Year 10 after start of data collection
Final report of study results*	Estimated 1 year after end of data collection

* timelines may change depending upon Pharmacovigilance Risk Assessment Committee (PRAC) protocol approval date

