9.7 Data Analysis

The Full Population will be all patients enrolled.

The Safety Population will include all patients enrolled who have taken at least one dose of efgartigimod for the efgartigimod cohort and all patients enrolled into the non-efgartigimod cohort. All analysis will be based on the Safety Population.

Unless otherwise specified, categorical endpoints will be summarised using counts and percent; continuous endpoints will be summarised using mean, standard deviation, median, minimum and maximum values. Statistical analysis will be mainly descriptive in nature using metrics such as

incidence proportion, exposure-adjusted incidence rate, confidence intervals, etc. Details of the analysis plan will be specified in the Statistical Analysis Plan (SAP).

Primary objective

Descriptive statistics will be used to summarise the long-term safety of efgartigimod, including the occurrence of events of serious infections, in gMG patients treated with efgartigimod compared to gMG patients not exposed to efgartigimod. The number and percentage of patients with AEs/SAEs will be presented. The rate per person-year exposure with a 95% CI will be constructed using asymptomatic normal approximation.

Although no formal hypothesis will be tested in the study, statistical models will be used to test the difference of incidence between treatment cohorts (efgartigimod vs. comparator). Two base models which are widely used to model incidence proportion and incidence rate adjusted by potential confounders will be used:

1. To model incidence proportions, a logistic regression model will be used including patients with event vs. patients without event as the response variable and treatment group and country as covariates.
2. To account for varied follow-up time, a Cox regression model will be used with time to the first occurrence of event for each patient as the response variable, treatment group and country as covariates .

Countries with small sample sizes will be combined with other countries based on the geographic locations. Other covariates may be added to the above base models as described below.

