Balance of the baseline measures, including age, MG-ADL score and region matched at enrollment and other demographic and disease characteristics, will be assessed. The imbalanced measures which are considered to be potential confounders based on clinical judgement will be added to the above base models as covariates. If a large number of imbalanced potential confounders are identified after the enrollment is complete, a propensity score method will be applied instead. More details will be given in the SAP.

Subgroup analyses will be performed using descriptive statistics on the subset of patients who remained on efgartigimod throughout the duration of the PASS. In addition, subgroup analyses of treatment cycle per year or administration per year (four administrations in one cycle if not interrupted), subgroup analyses of time since the last administration of efgartigimod prior to the event occurrence in intervals of every 4 weeks will be performed, and subgroup analysis of patients using efgartigimod as add-on or single treatment will be performed if sample size allows. Since one patient may have multiple same events with different time to the last administration, one patient may be assigned to multiple time intervals.

Events of Interest

Statistical analysis of malignancy and other events of interest will follow the same method as those for serious infections

Exploratory objectives

Descriptive statistics will be used to summarise the long-term safety of efgartigimod for specific subgroups. The number and percentage of patients with AEs/SAEs will be presented. The rate per person-year exposure with a 95% CI will be constructed using asymptomatic normal approximation. This will be done for the following subgroups:

- immunocompromised patients and immunocompetent patients.
- patients treated with monoclonal antibodies and patients not treated with monoclonal antibodies.
- patients who have received live/attenuated vaccine and patients who have not received live/attenuated vaccine.
- patients with moderate to severe renal impairment and patients with normal renal function or mild renal impairment.

Missing values

No imputation will be applied to occurrence of serious infection, malignancy or other safety events.

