The study design includes an efgartigimod cohort and a comparator cohort of non-efgartigimod treated patients. The duration of the study is a maximum of 10 years (5 years of enrolment and 5 years of follow up). Over this time period, standard of care for the treatment of gMG is likely to evolve with the introduction of new medicinal products such as ultomiris (recently approved) and rozanolixizumab and zilucoplan (currently under review with an approval expected by end of 2023) and the potential for patients to switch treatments during this time. The comparator group, and indeed the efgartigimod group, will therefore be heterogenous in terms of treatments, thus limiting the interpretability of the results.

Furthermore, in countries where efgartigimod is marketed, it is likely that the efgartigimod cohort and the comparator cohort will differ in terms of disease severity with the more severe patients receiving efgartigimod. Thus, there will be an inherent selection bias. This could be solved by recruiting the comparator patients from countries where efgartigimod is not marketed. However, this will introduce further biases in terms of differing standards of care.

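### Section 9.7 admits confounders to the models only if they look imbalanced, so several modest same-direction imbalances can stay unadjusted and add up

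*Protocol*

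**What the plan says.** Protocol section 9.7 (Data Analysis) sets two base models for comparing the cohorts.

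- Logistic model: "patients with event vs. patients without event as the response variable and treatment group and country as covariates".
- Cox model: "time to the first occurrence of event for each patient as the response variable, treatment group and country as covariates".
- Further terms are optional: "Other covariates may be added to the above base models as described below".
- The entry rule: "The imbalanced measures which are considered to be potential confounders based on clinical judgement will be added to the above base models as covariates". A measure must therefore both be found imbalanced and be judged a potential confounder.
- The balance check covers the baseline measures, "including age, MG-ADL score and region matched at enrollment and other demographic and disease characteristics, will be assessed". Age and MG-ADL are thus candidates for entry and not fixed terms.
- The fallback: "If a large number of imbalanced potential confounders are identified after the enrollment is complete, a propensity score method will be applied instead".

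Malignancy and the other events of interest follow the same method as serious infection.

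Section 9.1 matches the cohorts on age (within 5 years), MG-ADL band and region. Section 9.9 says of the two cohorts that it is likely they "will differ in terms of disease severity with the more severe patients receiving efgartigimod", and calls this an inherent selection bias. Table 1 (section 9.3) lists among the baseline data past infections, immune status, MGFA class, eGFR and gMG treatments, all collected only where routine practice supplies them.

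**The concern.** Confounding by severity and by background immunosuppression is the main threat to an observational comparison of serious infection, and the protocol predicts the severity part itself. Yet the default models hold no severity measure and no infection risk factor. A variable's claim to adjustment rests on how different the cohorts happen to look, when it should rest on its known relation to treatment choice and infection.

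An imbalance screen judges variables one at a time, while bias accumulates across variables. If efgartigimod patients have slightly more steroid use, more immunosuppressants, more past infections and a slightly worse MGFA class, each difference may fall below the line while together they shift the hazard ratio. A strong predictor of infection with a small imbalance is also treated like a weak one. Such bias would tend to count against efgartigimod where sicker patients are channelled to it, and the reported interval would not reflect it.

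**Working it through.** **1. The plan's own figure.** Table 4 gives 84% power for 20% versus 31% with 270 per arm, two-sided alpha 0.05, normal approximation.
- Mean proportion 0.255. SE under the null = √(2 × 0.255 × 0.745 / 270) = 0.0375.
- SE under the alternative = √((0.20 × 0.80 + 0.31 × 0.69) / 270) = 0.0372.
- z = (0.11 − 1.96 × 0.0375) / 0.0372 = 0.98, so power = 83.65%.

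The figure reproduces and is not in dispute. It is an unadjusted two-proportion calculation.

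**2. The yardstick.** With equal follow-up and proportional hazards, 20% versus 31% implies HR = ln(0.69) / ln(0.80) = 1.66, and ln 1.66 = 0.509.

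**3. Bias formula.** For an omitted binary factor with prevalence p1 (efgartigimod) and p0 (comparator) and hazard ratio h, the approximate bias factor is [1 + p1(h − 1)] / [1 + p0(h − 1)]. Factors multiply if independent. All prevalences and hazard ratios in steps 4 to 7 are assumptions; the protocol gives none.

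**4. Two factors at a standardised difference of about 0.10.**
- 45% versus 50%, h = 2: 1.50 / 1.45 = 1.034 (standardised difference 0.100).
- 15% versus 18.7%, h = 2.5: 1.2805 / 1.225 = 1.045 (standardised difference 0.099).
- Product 1.08. ln 1.08135 / 0.509 = 0.078 / 0.509 = 15% of the yardstick on the log scale.

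**5. Four factors that pass a p < 0.05 screen.** Each is 45% versus 52%, h = 2.
- Balance test at 340 per cohort: z = 0.07 / √(2 × 0.485 × 0.515 / 340) = 1.83, p about 0.07.
- Each factor: 1.52 / 1.45 = 1.048. Four together: 1.048⁴ = 1.21.
- ln 1.2075 / 0.509 = 0.189 / 0.509 = 37% of the yardstick.
- The standardised difference is 0.14 each, so a 0.10 threshold would catch these. The outcome depends on a threshold the protocol does not set.

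**6. One factor, on the risk scale.** Prevalence 40% versus 47.5% (standardised difference 0.15, not significant at 270 per arm), comparator risk 20%, no drug effect. With an outcome risk ratio of 1.5, 2 or 3:

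| Risk ratio | Spurious risk increase (points) | Odds ratio | False-positive rate |
|---|---|---|---|
| 1.5 | 0.6 | 1.04 | 5.4% |
| 2 | 1.1 | 1.07 | 6.1% |
| 3 | 1.7 | 1.11 | 7.6% |

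A single sub-threshold factor does little; the harm comes from several.

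**7. What the screen would catch.** At 270 per arm, 60% versus 45% has standardised difference 0.30 and p = 0.0005; 25% versus 15% has 0.25 and p = 0.004. Any usual screen flags both.

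**The case against.** The strongest reply is that the rule works where it matters most. Section 9.9 predicts a difference in severity, and a marked difference is exactly what a balance check finds. Section 9.7 then says such measures will be added. Matching on age, MG-ADL band and region gives some control by design, and country in the models is finer than region. Selection rests on baseline measures, so nothing in the text lets infection results steer it. Section 9.7 and the ENCePP checklist both refer the detail to the SAP.

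Most of this stands, and it limits the size of the point. It does not remove it. The SAP can supply the balance metric, the threshold and the propensity method, but the protocol has already fixed the order: imbalance first, adjustment second. Matching covers severity only through three wide MG-ADL bands and covers no treatment, immune or infection-history factor. The fallback depends on the same screen.

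Three stronger readings are tempting and not supported:

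- **That large confounders go unadjusted.** With h = 2 and 2.5, the two imbalances in step 7 would bias the HR by 1.10 × 1.12 = 1.24 if ignored. Under 9.7 they would be flagged and, as evident infection risk factors, added.
- **That omitting prognostic factors wastes precision.** In logistic and Cox models, adding covariates does not generally shrink the standard error of the treatment coefficient, and covariates correlated with treatment tend to enlarge it.
- **That the first interim report, due "Year 4 after start of data collection", has no confounder control.** Section 6 does not say that this report contains model-based comparisons, and the covariate route has no timing limit. Only the propensity-score switch is unavailable before enrolment closes, planned for year 5.

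**Conclusion.** The point holds in limited form. Section 9.7 fixes an inferior selection rule: no confounder except country is sure of a place in either model, although section 9.9 expects channelling of sicker patients to efgartigimod. The residual bias comes from several modest imbalances in one direction, not from large ones. On assumed values it is a factor of about 1.08 (two factors at a standardised difference near 0.10) to 1.21 (four factors that pass a p < 0.05 screen), against an implied HR of about 1.66. These figures assume independent binary factors, all pushing the same way, with the stated prevalences and hazard ratios. Positively correlated factors adjusted in part, or a stricter threshold, would give less; more factors would give more. The analysis is described as mainly descriptive, but this is the comparison for the primary objective and the method is carried over to malignancy, so the rule is worth changing before comparative data accrue.

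**What to change.** In section 9.7, replace the imbalance condition with a core adjustment set named on subject-matter grounds from Table 1 and the demographics. An example is age, MG-ADL, country, sex, MGFA class, prior infections, immune status, and baseline corticosteroid, other immunosuppressant and monoclonal antibody use. Include it in both models whatever the observed balance, and in every report that compares the cohorts.

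Alternatively, make one pre-specified propensity-score method primary from the start. This suits rarer outcomes such as malignancy, where a long covariate list could overfit.

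Keep the balance tables as a diagnostic only. If eGFR is included, define its baseline for the comparator cohort by enrolment date, because Table 1 ties it to the start of efgartigimod.

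Cost: no new data items. The models gain parameters; at 20% incidence in 680 patients about 136 patients would have a serious infection (0.20 × 680), which can carry such a set. Some covariate values will be missing because variables are recorded only when routine practice provides them, so the missing-covariate rule in 9.7 will be used more often.

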9. RESEARCH METHODS

9.1 Study Design

This is a non-interventional, prospective, post authorisation safety study.

Patients with gMG who are expected to start treatment with efgartigimod at enrolment or are within their first cycle of efgartigimod at enrolment will be eligible to enrol into the efgartigimod cohort. Patients with gMG who have not been exposed to efgartigimod and for whom it is not planned to start treatment with efgartigimod at enrolment will be eligible to enrol into the non-efgartigimod cohort. It is anticipated that 340 patients will be enrolled in each cohort.

Patients will be treated and observed according to normal clinical practice. Participation in this study does not limit the physicians` clinical decision making as to the most appropriate treatment for the patient during the course of the study. No visits or investigations outside of normal clinical practice will be required. The enrolled patients will be followed prospectively until end of study participation, loss to follow up, consent withdrawal, or death, whichever comes first. All adverse events (AEs) will be collected throughout the duration of the study.

Enrolment of patients will be over a 5-year period. The follow up of patients will continue for 5 years from the time the last patient has been enrolled. Patients will be followed regardless of whether they continue or discontinue efgartigimod. Assuming a 5-year enrolment period this will allow for a maximum of 10 years of follow-up and a minimum of 5 years. A patient will be considered to be an efgartigimod exposed patient if he/she has received at least one dose of efgartigimod.

In order to minimise heterogeneity between the two cohorts, patients in the efgartigimod cohort will be matched at enrollment with a patient in the non-efgartigimod cohort for the following criteria:

- Age (\pm 5 years)
- Myasthenia Gravis -Activities of Daily Living (MG-ADL) score (0-5, 5-9, and >9) ([Wolfe, 1999](#))
- Region (within EU and within US)

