- **Recovered/Resolved with sequelae** – The event has reached a state where no further changes are expected, and the residual symptoms are assumed to persist. An example is hemiparesis after stroke.
The stop date of the event must be recorded. In case of an SAE, the sequelae should be specified.
- **Fatal** – The subject has died as a consequent of the event.
- **Unknown** – Unknown to investigator, e.g., subject lost to follow up.

Action taken:

- **Withdrawal** - the permanent discontinuation of efgartigimod when the participant stops receiving efgartigimod before the end of the study and does not resume receiving efgartigimod.

- **Interruption-** the temporary discontinuation of efgartigimod when the participant discontinues receiving efgartigimod before the end of the study and resumes once the cause for the discontinuation has been resolved

Pregnancy

If pregnancy is reported, the treating physician will record the pregnancy information on the appropriate form and submit it to the sponsor within 7 calendar days of learning of the pregnancy in the female participant or the female partner of the male participant. The participant and pregnant female partner, if consented, will be followed to determine the outcome of the pregnancy. The treating physician will collect follow-up information on the participant/pregnant female partner and the neonate and forward it to the sponsor. While pregnancy itself is not considered an AE or SAE, any pregnancy complication or elective termination of a pregnancy for medical reasons will be reported as an AE or SAE. Abnormal pregnancy outcomes (e.g., spontaneous abortion, fetal death, stillbirth, congenital anomalies, ectopic pregnancy) are considered SAEs and will be reported accordingly.

Contact details to report AEs/SAEs and Pregnancies to the sponsor:

•**Email:** [contact]

•**[contact]

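### The planned subgroup of patients who never stop efgartigimod drops those whose event ended treatment, so it understates the on-treatment event rate

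*Protocol*

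**What the plan says.** Section 9.7, under the primary objective, lists the subgroup analyses. The first reads: "Subgroup analyses will be performed using descriptive statistics on the subset of patients who remained on efgartigimod throughout the duration of the PASS". The same paragraph adds analyses by cycles or administrations per year, by add-on or single use, and by time since last dose.

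Four other parts of the protocol bear on this subgroup:

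- **Analysis set (9.7).** "All analysis will be based on the Safety Population". For the efgartigimod cohort, this set needs only one dose.
- **Follow-up (9.1).** "Patients will be followed regardless of whether they continue or discontinue efgartigimod". Given five years of enrolment, "this will allow for a maximum of 10 years of follow-up and a minimum of 5 years". Observation runs "until end of study participation, loss to follow up, consent withdrawal, or death, whichever comes first".
- **Stopping because of an event (11.1).** One action that can be recorded for an adverse event is withdrawal, defined as "the permanent discontinuation of efgartigimod when the participant stops receiving efgartigimod before the end of the study" with no later resumption. Table 1 in section 9.3 also collects the reason for a permanent stop.
- **Exposure (9.3).** Administration dates are collected, and exposure is taken to last 56 days (plus or minus 3) beyond the last dose.

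Section 9.9 on limitations does not mention selection by continued treatment.

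**The concern.** The subset is defined by what happens after enrolment, over as much as ten years. A patient whose serious infection leads to a permanent stop does not qualify. That patient's infection leaves the numerator and the earlier treated time leaves the denominator. A patient with the same infection who carries on stays in. The events kept are therefore only those that treatment survived.

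Section 7 names the long-term safety of efgartigimod as missing information, and it is part of the primary objective. A reader who wants to know what happens to patients on prolonged treatment will look at this subset. Its rates will lean towards reassurance, and the lean is strongest for the events most likely to end treatment. The SAP can add detail but cannot remove the bias while keeping this definition.

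**Working it through.** **The plan's own figures.** The protocol gives no figure for this subset. Its sample-size figures do reproduce. For 20% against 31% with 270 per arm, the pooled standard error is sqrt(2 × 0.255 × 0.745 / 270) = 0.0375 and the unpooled one is sqrt((0.16 + 0.2139) / 270) = 0.0372. Then z = (0.11 − 1.96 × 0.0375) / 0.0372 = 0.98, which is 83.7% power against the stated 84%. Enrolment is 270 / 0.8 = 338 against the stated 340.

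**Inputs.**
- Serious infection proportion of 20% (section 9.5).
- Follow-up of 5 to 10 years (section 9.1). Spread evenly, which is an assumption, the mean is 7.5 years.
- Constant hazard (assumption): λ = −ln(0.80) / 7.5 = 0.0298 per year, or 2.98 per 100 patient-years.
- q, the share of serious infections that end treatment for good. The protocol does not give it; assumed 0%, 10%, 25% and 50%.
- Stopping for other reasons: assumed 0%, 5% or 15% per year.

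**Equal risk in all patients.** Infections that end treatment arise at rate qλ and the others at rate (1 − q)λ, independently. Staying in the subset requires none of the first kind and says nothing about the second. So:

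subset rate = (1 − q) × λ

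subset proportion over 7.5 years = 1 − 0.80^(1 − q)

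**Uneven risk.** If patient risk follows a gamma distribution with variance 1, continuers are also a lower-risk group. The subset rate over the true rate is then about (1 − q) / (1 + qλF). With F = 7.5, λF = 0.223. At q = 25% this is 0.75 / 1.056 = 0.71, a shortfall of 29%.

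| q | Subset rate per 100 patient-years, formula | Simulated (200,000 patients per scenario) | Shortfall, equal risk | Shortfall, uneven risk | Subset proportion |
|---|---|---|---|---|---|
| 0% | 2.98 | 2.98–3.00 | 0% | 0% | 20.0% |
| 10% | 2.68 | 2.68–2.71 | 10% | 12% | 18.2% |
| 25% | 2.23 | 2.19–2.24 | 25% | 29% | 15.4% |
| 50% | 1.49 | 1.48–1.51 | 50% | 55% | 10.6% |

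A higher background rate matters only when risk is uneven. Section 9.5 cites a population-based cohort with 33.4% over a mean of 5.4 years, so λ = −ln(0.666) / 5.4 = 0.0753. The uneven-risk shortfalls then become about 15%, 35% and 61%.

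**Stopping for other reasons.** This leaves the subset rate unbiased but shrinks the subset. With q = 0, 340 patients become about 234 at 5% per year and about 113 at 15% per year.

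**The alternative.** Keeping all treated patients, counting person-time up to stopping and including the event that caused the stop, the simulated rate is 2.9 to 3.0 for every q.

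**The case against.** **The main result does not use this subset.** The cohort comparison, including the logistic and Cox models, rests on the Safety Population with follow-up after stopping. Every event that ends treatment stays in it. This stands, and it limits the severity.

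**The size is unknown.** The bias is zero at q = 0 and the protocol gives no q. This also stands: the protocol foresees such stops but does not quantify them, so only the direction for q above zero is certain.

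A reader might infer more, in five ways that the documents do not support.

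- *The subset will look low beside the whole cohort.* Not necessarily, because the whole-cohort rate includes off-treatment time. If risk is 31% on treatment and 20% off it, q is 10% and other stopping is 15% per year, simulation gives 4.4 per 100 patient-years for continuers, 4.1 for the whole cohort and 4.9 for true on-treatment time.
- *Patients who die on treatment are dropped too.* This depends on the reading. If the words mean the whole study period, they are dropped. If they mean each patient's own follow-up, which staggered entry makes plausible, such patients stay and only stoppers are lost.
- *This is the only analysis of sustained exposure.* The protocol also plans analyses by cycles or administrations per year, and rates per patient-years exposed.
- *Continuous exposure is the named information gap.* Section 7 speaks of long-term safety, and dosing is in cycles of varying frequency.
- *The companion display will show a false peak after dosing.* The protocol says that "subgroup analyses of time since the last administration of efgartigimod prior to the event occurrence in intervals of every 4 weeks will be performed" and states no denominator. A full four-dose cycle with at least eight weeks before re-treatment puts 21 + 28 = 49 days in the first interval and 28 in the second, a ratio of 1.75. That pattern is an assumption. Section 9.7 lists exposure-adjusted rates among its metrics and leaves detail to the SAP, so a missing denominator here is not an error.

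**Conclusion.** The point holds for the continuer subset alone. As defined, it understates the true on-treatment rate of any event that sometimes ends treatment, by about the share of events that do so: about 10%, 25% and 50% at those assumed shares, and 12%, 29% and 55% under the uneven-risk assumption. There is no bias in the rate if no event ends treatment. Section 9.7 applies the same methods to malignancy and the other events of interest, so the reasoning carries over, with a share specific to each event.

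These sizes rest on a constant hazard, evenly spread follow-up and treatment modelled as on or off rather than in cycles. The direction for q above zero follows from the definition. Because the subgroup is descriptive and the main comparison is unaffected, this is a moderate problem that is cheap to correct.

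**What to change.** In section 9.7, replace the continuer subset with an on-treatment analysis of all efgartigimod patients in the Safety Population:

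- Count events and person-time while exposed, using the collected administration dates and the protocol's own window of 56 days after the last dose. Apply the same window to events and to person-time, and say how gaps between cycles that outlast it are handled.
- Include the event that led to stopping.
- Show rates by time since first dose, so that long-term exposure is visible without selecting on it.
- Report how many events of each type led to permanent discontinuation, from the action-taken and reason-for-stopping fields.

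If the display by 4-week interval is kept, report events over the person-time that all exposed patients spent in each interval.

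The cost is protocol and SAP wording plus programming to split person-time. No new data are needed and the study size does not change.

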gMG treatments at or following enrollment (excluding efgartigimod)	
 Drug name, dose, start and stop dates 
 Acetylcholinesterase inhibitors Corticosteroids Other Immunosuppressants (specify) Monoclonal antibodies (specify) Plasmapheresis/plasma exchange acute Plasmapheresis/plasma exchange chronic IVIg therapy acute IVIg therapy chronic Other 	✓	✓

Category	Variables	Baseline	Follow up
Efgartigimod treatment	
 • Date of administration • Reason for interruption during cycle of treatment • Reason for permanent discontinuation whilst on study 	✓	✓
Other comedications at or following enrollment for conditions other than gMG	
 • Drug name, start and stop dates • Indication 	✓	✓
Live/attenuated vaccinations 2 months prior to enrollment to 2 months after last Vyvgart dose	
 • Live/attenuated vaccine 
 ○ Vaccine ○ Date 	✓	✓
Adverse Events (AEs)/Serious Adverse Events (SAEs)	
 • AEs, SAEs 		✓
Events of interest	See Table 2		✓

*All variables will be collected ONLY if available as part of routine clinical practice

A patient will be considered to be an efgartigimod exposed patient if he/she has received at least one dose of efgartigimod.

Additionally, taking into account the variable follow up time and time interval between cycles, the following will be measured for efgartigimod:

- Number of administrations per year
- Total duration of the exposure
- Total number of administrations

The exposure time window of efgartigimod is 56 days +/-3 days after the last dose.

Events of interest in this study will be pre-specified as per [Table 2](#) below.

Table 2: Pre-specified events of interest

Event of interest	Definition	Measurement
Serious infection	Any serious adverse event coded to the Medical Dictionary for Regulatory Activities (MedDRA) System Organ Class (SOC) of Infection and Infestation. See Section 11 for definition of Serious.	Proportion of patients who report serious infections during the course of the study in the efgartigimod treated cohort compared to the non-efgartigimod cohort. Incidence rate of serious infections per patient-years exposed in the efgartigimod treated cohort compared to the non-efgartigimod cohort.

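### The sustained-use subgroup in Section 9.7 is selected on later persistence, so events that end treatment drop out of it and risk under sustained use is understated

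*Protocol*

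**What the plan says.** Among the subgroup analyses under the primary objective, Section 9.7 plans: "Subgroup analyses will be performed using descriptive statistics on the subset of patients who remained on efgartigimod throughout the duration of the PASS". It sets the same methods for malignancy and the other events of interest.

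The main analyses rest on a different population. Section 9.7 states: "All analysis will be based on the Safety Population". For the efgartigimod cohort this means everyone with at least one dose. Section 9.1 adds: "Patients will be followed regardless of whether they continue or discontinue efgartigimod". Individual follow-up ends as follows: "The enrolled patients will be followed prospectively until end of study participation, loss to follow up, consent withdrawal, or death, whichever comes first". Its planned length is also given: "Assuming a 5-year enrolment period this will allow for a maximum of 10 years of follow-up and a minimum of 5 years".

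Exposure is recorded in some detail. Table 1 in Section 9.3 collects administration dates and "Reason for permanent discontinuation whilst on study". The same section defines a window: "The exposure time window of efgartigimod is 56 days +/-3 days after the last dose". Section 9.7 also plans "subgroup analyses of time since the last administration of efgartigimod prior to the event occurrence in intervals of every 4 weeks will be performed", and subgroups by cycles or administrations per year and by add-on or single use.

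**The concern.** The subset is defined by something that happens after baseline and that the safety outcome can itself cause. The protocol foresees this: permanent withdrawal of efgartigimod is one of the actions recorded for an adverse event (Section 11.1), and the reason for permanent discontinuation is collected. A patient whose infection or cancer ends treatment fails the membership rule and leaves both numerator and denominator.

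Section 7 names long-term safety as missing information, and it is part of the primary objective. The main comparison classes a patient as exposed after a single dose and follows patients after they stop, so it mixes time on and off the drug. A reader who wants to know what happens under continued use would turn to this subset. Neither Section 9.7 nor Section 9.9 warns that it is selected on outcome.

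**Working it through.** **The plan's own figures.** The protocol gives no figure for the subset. Its sample-size figures reproduce and are not at issue:
- Power for 20% against 31% with 270 per arm is 83.7% (pooled variance) or 84.0% (unpooled); Section 9.5 states 84%.
- 270 / (1 − 0.20) = 337.5, or 338 rounded up; Section 9.5 states 340.

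**Inputs.**
- p = 20%, the serious-infection proportion assumed in Section 9.5.
- n = 340 per cohort, Section 9.5.
- q = share of patients with a serious infection who permanently discontinue because of it. The documents do not give it, so it is assumed and varied.

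**Proportion in the subset.** Of n patients, np have an event and npq of them are removed. If all other stopping is unrelated to infection and to length of follow-up:

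p_sub = (np − npq) / (n − npq) = p(1 − q) / (1 − pq)

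With n = 340, np = 68:
- q = 0: 68/340 = 20.0%
- q = 0.10: 6.8 removed, 61.2/333.2 = 18.4%
- q = 0.25: 17 removed, 51/323 = 15.8%
- q = 0.50: 34 removed, 34/306 = 11.1%

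**Check by simulation.** Entry was uniform over 5 years, with 5 to 10 years of follow-up. The infection rate was set at −ln(0.8)/7.5 = 0.0298 per year, which is 20% over a mean potential follow-up of 7.5 years. Unrelated stopping of 3, 5 or 10% per year was assumed. At 5% per year, first-event rates per 100 patient-years were:

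| q | Persister subset | On-treatment, all starters |
|---|---|---|
| 0 | 2.96 | 2.96 |
| 0.10 | 2.70 | 2.97 |
| 0.25 | 2.30 | 2.98 |
| 0.50 | 1.56 | 2.96 |

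The rate in all patients over full follow-up was 2.97 to 2.98 in these rows. Subset rates at 3% and 10% per year were almost the same (1.58 and 1.57 at q = 0.50).

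Subset proportions in the simulation were slightly below the formula: 18.0%, 15.6% and 10.9% at 5% per year. The reason is that patients with shorter follow-up are more likely still to be on drug at the end. Even at q = 0 the proportion was 19.6%, while the rate was unaffected.

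The on-treatment result is this clean because stopping for other reasons was simulated as independent of infection.

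**The case against.** The strongest reply is that the study's safety conclusion does not rest on this subset. The logistic and Cox models use the Safety Population, and patients are followed after stopping. This stands. A reader might infer that the flaw biases the main cohort comparison towards safety or could hide a real excess there. The documents do not support that.

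Four further points limit the concern:
- **Other exposure analyses.** Rates per patient-years exposed are planned in all dosed patients (Table 2, Section 9.7), and the ENCePP checklist defers exposure detail to the SAP. An on-treatment rate may already be intended, so a missing censoring rule is no fault in itself. What remains is that the protocol specifies the persister subset, and the other subgroups do not describe sustained use.
- **Who is removed.** A reader might infer that everyone who died or left the study is excluded. If the duration of the PASS means each patient's own participation, those who died or left while on drug stay in. Section 11.1 also separates temporary interruption from permanent withdrawal, and treatment is given in cycles, so a delayed cycle need not disqualify. Only event-driven permanent discontinuation removes a patient under either reading.
- **Relative risk.** A reader might set the subset beside the unfiltered comparators and conclude that a raised rate ratio could be masked or reversed. Section 9.7 plans only descriptive statistics for the subset and states no such contrast.
- **Size.** q is unknown, and at q = 0.10 the effect is modest.

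A fair objection to the obvious remedy also stands: if every outcome were censored 56 days after the last dose, malignancies diagnosed later in patients who stopped would be lost.

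**Conclusion.** The concern holds for this one supplementary, descriptive subgroup. Event-driven permanent discontinuation biases its serious-infection and malignancy figures downward whenever it occurs. For serious infection at the planned 20%, the subset would show about 18.4%, 15.8% or 11.1% at q = 0.10, 0.25 or 0.50. These sizes rest on assumed q and on other stopping being unrelated to risk; only the direction of this mechanism is certain. The documents give no basis for a malignancy figure. The main Safety Population comparison is unaffected. The subset should not carry any conclusion on long-term safety.

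**What to change.** In Section 9.7, replace the persister subset as the sustained-use analysis with an on-treatment person-time analysis of all dosed efgartigimod patients:
- Start at first dose, or at enrolment if dosing began earlier, because adverse events are collected only from consent.
- Count events and person-time to last dose plus the protocol's own 56-day exposure window, and censor there. State how the ±3 days is applied.
- Show rates by time since first dose, with reasons for discontinuation.

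Keep the ever-exposed, full follow-up analysis beside it, especially for malignancy, which may be diagnosed after the window closes. If the persister subset is retained, define what remaining on efgartigimod means, label the subset as descriptive and selected on outcome, and do not use it to conclude on long-term safety.

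The cost is a few lines in Section 9.7 and one additional set of tables; dosing dates and stop reasons are already collected. The drawback is that on-treatment censoring may itself be informative, if patients stop because their risk is changing. That is a further reason to report both analyses together.
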